## STUDY DESIGN

Overview. In a 6-week pilot RCT, we will assess the feasibility and preliminary efficacy of an immersive mindfulness VR treatment (RelieVRx) versus a non-immersive sham VR control (sham VR) for the treatment of pain and OUD. We will recruit 40 adults with OUD and chronic pain enrolled in an MMTP and randomize 1:1 to RelieVRx vs sham VR. Over 6 weeks, participants in both groups will participate in 20-30 minute VR sessions twice per week at the MMTP. Over the course of the study, the research team will conduct pain and psychological assessments at baseline, 3 weeks, and at the study conclusion at 6 weeks. We will also explore changes in stress and inflammatory saliva and blood biomarkers at baseline, 3 weeks and 6 weeks. To assess feasibility, we will examine recruitment and retention and assess patient satisfaction. Our preliminary efficacy co-primary outcomes are (1) change in pain intensity and (2) change in opioid craving between treatment groups at 6 weeks. Secondary outcomes will include changes in pain interference, physical functioning, depression, anxiety, sleep quality, illicit opioid use, and prescription opioid use. In a separate aim, we will also explore changes in stress and inflammatory markers over the course of the trial.

Setting and Participants. We will recruit and conduct study visits at one Montefiore Opioid Treatment Program (OTP). Montefiore has the largest network of OTPs in New York State. Three of the five Montefiore OTPs comprise the Montefiore Division of Substance Abuse (DoSA) Wellness Centers; in total, these sites serve approximately 3,000 individuals. Electronic health data indicates that of 945 people with a chronic pain diagnosis who are on methadone for OUD, 555 (59%) are Male, mean age is 58.3, 566 (60%) are Hispanic, 170 (18%) are Black, and 140 (15%) are White.

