Participants: We will enroll 40 participants. As the narration of the VR device is only provided in English at this time, we require English proficiency for this pilot trial. Inclusion criteria: 1) ≥18 years old, 2) English proficiency; 3) receiving methadone treatment for DSM-5 confirmed OUD in the Montefiore network for at least 12 weeks, with no dose change in 14 days to ensure treatment stability; 4) chronic pain of at least moderate pain severity (score ≥4 on the Pain, Enjoyment of Life, and General Activity (PEG) scale); 5) willingness to participate in all study components; and 6) ability to provide informed consent, assessed using consent teach-back. Exclusion criteria: 1) conditions that could make participation in VR hazardous or cause adverse effects (current or prior diagnosis of epilepsy, seizure disorder, dementia, or migraines, any medical condition predisposing to nausea or dizziness, hypersensitivity to flashing light or motion), 2) conditions that could prevent proper use of the VR headset (stereoscopic vision or severe hearing impairment, or injury to eyes, face, or neck that prevents use of the VR headset), and 3) acute exacerbation of psychiatric conditions that preclude the ability to participate in the study. Pregnant patients are NOT excluded from the trial as there are no contraindications to their use of a VR device, but we are not specifically targeting pregnant patients for this study nor are we testing for pregnancy.

**Recruitment, Screening, and Randomization**. Recruitment will be active and passive in the OTP. Based on our team's prior DoSA trials and the scope of this current project, we anticipate enrolling 1-2

participants weekly. Research staff will enroll from one DoSA site for the duration of the trial; we will plan our recruitment strategy in conjunction with other IMPOWR-ME trials as to not recruit from the same pool of patients at a site at the same time. We expect retention of approximately 85% based on our groups prior DoSA trials.  **Screening:** After obtaining written consent, we will administer a screening questionnaire. Potentially eligible subjects will then complete a written informed consent process including discussion of procedures and risks and benefits before being randomized. Consent will occur in a private area of the OTP. **Randomization**: Randomization will occur using block randomization (blocks

of 4) to two conditions in a 1:1 ratio.

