**Description of** intervention and control. Both intervention and control arms will utilize a Pico G2 head-mounted VR device with preinstalled software. RelieVRx incorporates evidence-based principles of cognitive behavioral therapy and mindfulness to provide pain neuroscience education and to train users on evidence-based pain and stress management strategies with interactive and immersive exercises and experiences. In total, RelieVRx combines biopsychosocial pain education, diaphragmatic breathing training, relaxation exercises.

| Table 1. Overview of Dat
Domain | Measure  | Source        |
|------------------------------------|--|---------------|
| Feasibility Outcomes               | 1 Transmit   | Source        |
| Percent screened                   | Proportion of total participants contacted who are screened  | RL            |
| Percent consented                  | Proportion of total participants screened who consent  | RL            |
| Percent retained                   | Proportion of total participants consented who complete  | RL            |
| r creent retained                  | study  |               |
| Patient satisfaction               | Global impression of change scale   | S             |
| Preliminary Efficacy Out           |  |               |
| Pain intensity (co-
primary)    | PEG,  PROMIS Pain Intensity subscale   | S             |
| Opioid craving (co-
primary)    | Opioid Craving Visual Analog Scale    | S             |
| Quality of life                    | PROMIS Physical Functioning, PROMIS PROPr Fatigue,
Cognitive Function, Social Function   | S             |
| Stress                             | Perceived stress scale   | S             |
| Pain interference                  | PROMIS Pain Interference Subscale, 61 PEG   | S             |
| Pain history and                   | Pain screening questions, Michigan pain body map  , use   | S             |
| characteristics                    | of medications and treatments, chronic pain acceptance,  pain self-efficacy  , pain catastrophizing                   |               |
| Mood symptoms                      | PROMIS PROPr Depression, Anxiety    | S             |
| Sleep quality                      | PROMIS Sleep Disturbance 6A + Sleep Duration    | S             |

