Potentially eligible subjects will then complete a written informed consent process with HIPAA authorization including discussion of procedures and risks and benefits before being randomized. Consent will occur in a private area of the OTP. The RA will perform consent teach-back to assure that participants are aware of the details of the consent. Participants who give consent and are randomized will then complete the first study visit at a convenient time. Participants will be reimbursed \$50 for their participation at each study assessment. If they choose to participate in the optional qualitative component, they will be reimbursed an additional \$30.

Tests and procedures, including blood draws and saliva samples, performed at study assessments will not be billed to participants.

Patient privacy protection. We will strip patients' protected health information from all data before conducting analyses. As in prior studies we have conducted, we will have a "name-based" and an "ID-based" identification system that will remain separate. In the name-based system, all documents that have patient identifiers will be filed together. Some of these documents will have participants' signatures (e.g., consent forms). In the ID-based system, all documents that do not include identifying information or signatures will use participants' unique study IDs (rather than names) and will be filed together. All forms will contain either a "name-based" or an "ID-based" identifier, but never both. There will be only one electronic document that links participants' names to their study IDs; only the study staff will have access to this document, which will be password protected and kept on password-protected servers.

Study data will be kept in a password-protected, encrypted file on password-protected servers that are backed up daily. No one but the study team will have access to study data. Publication or presentation of study results will not include information that would allow for identification of providers or patients.

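### Randomization comes before the week-0 visit, so the baselines for both co-primary outcomes are taken after allocation; reversing the order would cost little

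*Combined protocol and SAP*

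**What the plan says.** Under Recruitment, Screening, and Randomization, a screening questionnaire is followed by full consent and then allocation: "Potentially eligible subjects will then complete a written informed consent process including discussion of procedures and risks and benefits before being randomized". The Informed Consent section repeats this and adds what comes next: "Participants who give consent and are randomized will then complete the first study visit at a convenient time". No section places a study assessment before randomization.

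The Overview states that "the research team will conduct pain and psychological assessments at baseline, 3 weeks, and at the study conclusion at 6 weeks". Data sources, measures, and management puts the assessments at weeks 0, 3 and 6, with every measure taken each time. The first study visit is therefore the week-0 baseline.

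The co-primary outcomes are the 6-week changes in pain intensity and opioid craving. Table 1 lists the PEG and the "PROMIS Pain Intensity subscale" for pain, and the "Opioid Craving Visual Analog Scale" for craving. The Analytic plan takes the time-by-arm interaction as the effect.

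Two features bear on how much the order matters. Eligibility requires "chronic pain of at least moderate pain severity", scored on the PEG, so one pain score exists before allocation. And "Both intervention and control arms will utilize a Pico G2 head-mounted VR device with preinstalled software", so the hardware does not reveal the arm.

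**The concern.** A baseline is protected from the effects of allocation when it is recorded before allocation, or when nobody involved can know the arm. The first condition fails here and the second is not stated. The documents do not say whether participants or assessors are masked, when the arm is revealed, or how long the gap to week 0 may be.

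Both co-primary outcomes are self-reported. A participant who learns the arm may rate pain or craving differently from hope or disappointment, and an assessor who knows it may influence the answers. Such a shift at week 0 would enter the estimated change. The PEG eligibility score partly covers pain, but it is not named as the baseline. No pre-allocation score is described for PROMIS Pain Intensity or for craving.

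A second consequence does not depend on masking. Someone lost between randomization and week 0 has been allocated but contributes no outcome data, in a trial of 40.

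**Working it through.** **The plan's own figure.** The nearest stated figure is the 70% power in the Power analysis. It does not reproduce: d = 0.49 with 20 per arm at a two-sided 5% level gives 33% (exact t). Visit order is not an input to power, so that is a separate matter. Only d and the mean changes are used below.

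**Inputs from the documents.** Mean changes of 2.2 and 1.2; d = 0.49; 20 per arm; visits at 0, 3 and 6 weeks; 85% expected retention, which is 17 per arm.

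**Assumptions not in the documents.** The arm is known at week 0; a shift s of 0.1 to 0.5 points occurs in one arm; a fraction p of it persists to week 6; the test is two-sided at 5%; d is standardized by the SD of change; time is linear and data are complete; there is no true effect.

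**How the shift enters.** Deviations of visit time from the mean are -3, 0 and +3, with sum of squares 18. The slope is (3·y6 - 3·y0)/18 = (y6 - y0)/6. Over 6 weeks the contrast is y6 - y0, so the visit weights are -1, 0 and +1. The bias has absolute size s × (1 - p): all of s if the shift has gone by week 6, and none if it persists fully. Its sign depends on which arm is shifted and in which direction.

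**Standard error for pain.** SD of change = (2.2 - 1.2)/0.49 = 2.04. SE = 2.04 × √(2/20) = 0.645 at 20 per arm, and 2.04 × √(2/17) = 0.700 at 17 per arm.

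**False-positive rate.** This comes from a noncentral t with noncentrality s(1 - p)/SE, on 38 df (20 per arm) or 32 df (17 per arm). For example, s = 0.25 and p = 0 gives 0.25/0.645 = 0.39.

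| Setting | s = 0.1 | s = 0.25 | s = 0.5 |
|---|---|---|---|
| 20 per arm, shift gone (p = 0) | 5.3% | 6.7% | 11.8% |
| 20 per arm, half persists (p = 0.5) | 5.1% | 5.4% | 6.7% |
| 20 per arm, fully persists (p = 1) | 5.0% | 5.0% | 5.0% |
| 17 per arm, shift gone | 5.2% | 6.4% | 10.7% |
| 20 per arm, shift gone, SD 1.5 | 5.5% | 8.1% | 17.7% |
| 20 per arm, shift gone, SD 3.0 | 5.1% | 5.8% | 8.1% |

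A simulation of the linear time-by-arm contrast (20 per arm, 40,000 runs) agrees: 4.9% with no shift; 5.4%, 6.8% and 11.6% for the first row; and 4.9% for s = 0.5 with full persistence.

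**Craving.** The documents give no SD, so the shift is expressed in SD-of-change units. Shifts of 0.05, 0.10 and 0.20 that do not persist give 5.3%, 6.1% and 9.5% at 20 per arm.

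**Loss before week 0.** The rate is not given. Each person is 1/40 = 2.5% of the sample. If k are lost from one arm, the SE is multiplied by √[(1/20 + 1/(20 - k))/(2/20)], which is 1.013, 1.027 and 1.043 for k = 1, 2 and 3.

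**The case against.** The strongest reply is that no bias has been shown. The comparator is a sham on the same headset with content matched for length, and week 0 is when a participant has least on which to base a guess. This is a fair inference, but the plan does not state masking, so it remains an inference.

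The larger error rates also need an unfavourable combination: the largest assumed shift, in one arm, gone by week 6. Knowledge of the arm does not vanish, so some persistence is plausible and the half-persistence row may be nearer the mark. That stands. So does the point that the trial's main purpose is feasibility, which makes a modest move in nominal error less decisive. However, the estimates are also meant to inform a later application, and a shifted baseline would carry into them.

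The loss effect is small, and retention already counts it, since its denominator is everyone who consented: "Proportion of total participants consented who complete".

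Reordering does not by itself secure concealment. In fixed blocks of 4, the fourth allocation is always determined by the others, and the third is determined with probability 1/3. That is (1 + 1/3)/4 = one third of allocations, predictable to staff who know the block size and earlier arms. A sentence withholding the arm until week 0 is complete would deal with reporting bias without reordering, but it would not prevent loss between allocation and baseline.

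**Conclusion.** The point holds. As written, both co-primary baselines follow allocation, with no interval limit and no statement that the arm is withheld. The resulting bias is unknown and may be zero: it is zero if the arm is unknown at week 0, or if any shift persists fully. Under the assumptions above, pain's false-positive rate at SD 2.04 and 20 per arm is 5.3% to 11.8% in the worst case and 5.1% to 6.7% with half persistence. Craving is the less protected outcome because it has no described pre-allocation score. Losing one to three people from one arm before week 0 raises the SE by 1.3% to 4.3%. The change is worth making because it is cheap and removes post-allocation measurement of the baseline, not because a large bias has been demonstrated.

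**What to change.** In Recruitment, Screening, and Randomization and in Informed Consent, state the order as consent, complete week-0 assessment, then randomization at the end of that visit or just before the first VR session. State that all participants so randomized will be analysed. It would help to say in the same place who knows the allocation list and that the next allocation is concealed from staff doing the week-0 assessment.

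The cost is a change of wording and site workflow, with no added visit type, test or staff. The downside is that a few people may complete week 0 and not be randomized. Each costs the $50 payment, a 30-60 minute assessment and one set of blood and saliva samples, with possible assay and biobanking. For an assumed 1 to 4 such people, payments are $50 to $200. If 5% to 15% were lost at this step, 43 to 48 week-0 visits would be needed to randomize 40, which is 3 to 8 extra and $150 to $400. At the planned 1-2 enrolments a week, replacing 3 to 8 people would take about 1.5 to 8 weeks. Randomizing at the end of the same visit should keep this loss near zero. The text should also make clear that the target of 40 means 40 randomized.

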**Data sources, measures, and management.** Study assessments will take place onsite at the OTP at weeks 0, 3, and 6 and last 30-60 minutes. Participants will receive \$50 compensation at each study assessment. We will track the number of patients screened, eligible, consented, and retained. During assessments, participants will answer surveys and submit saliva and blood. In addition, we will extract information from the Montefiore EMR, SMART EMR (methadone dosage), and from the New York State Prescription Monitoring Program (PMP). Study measures are listed in Table 1; where possible we align our measures with IMPOWR CDEs and with IMMPACT recommendations for study of chronic pain. All measures will be examined at each study visit, at 0, 3 and 6 weeks. All study assessment data will be managed in REDCAP, a well-established, HIPAA-compliant web-based surveying platform and database. During twice weekly VR sessions, we will also conduct before and after surveys to ask about experiences during VR exercises not taking more than 5 minutes; these will be paper based, scanned, and uploaded to Montefiore BOX, a HIPAA-compliant online cloud storage service. A portion of blood will also be bio-banked to facilitate future biomarker analyses. We will conduct an optional qualitative interview exploring experiences in the trial at the conclusion of the trial; participant interviews will be recorded and transcribed for analysis.

**Informed Consent.** The RA will screen all potential participants for inclusion and exclusion criteria in a private area of the MMTP. First, we will obtain written consent to administer a screening questionnaire. Screening questionnaire questions will focus on inclusion and exclusion criteria, pain history, and also ask about prior use of virtual reality devices. The initial screening questionnaire will take 15 minutes. Participants will not be reimbursed for the screening questionnaire. Written consent and the initial screening questionnaire will occur in a private area of the MMTP.

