**Analytic plan.** Feasibility: Feasibility outcomes will be measured as proportions. Preliminary Efficacy: To examine the association between treatment arm and the co-primary outcomes, we will use separate 2-level mixed-effects linear regression model with the treatment arm as a mixed effect with participant-specific random intercepts to account for hierarchical data. The difference in trends of pain intensity and opioid craving will be represented by the time-by-arm interaction. For secondary outcomes and stress and inflammation exploratory outcomes, we will use a similar strategy; where outcomes are dichotomous, we will use 2-level mixed effects logistic regression models.

We will use thematic analysis to analyze transcripts in the qualitative study.

**Power analysis**. The primary purpose of this study is to test feasibility and to generate preliminary data for a future R01 application. We are able to enroll 40 participants in the pilot RCT given our resources and given the time of this study. We base our conservative power analysis on t-tests of change in our pain intensity preliminary efficacy outcome and use effect size estimates from a study of RelieVRx. In that study, the pre-post difference in pain intensity was 2.2 in the treatment group and 1.2 in the control group. Given the effect size of d=0.49, and 20 participants in each arm, we will have 70% power to detect a difference of this magnitude or larger. We expect to have greater statistical power using mixed effects linear regression models with repeated measures over time.

**Risks/Benefits**. We expect the major risks to be associated with the VR technology. VR can sometimes cause "cybersickness" in some patients, especially when playing or experiencing fast moving games or videos. RelieVRx is a much less intense program designed to minimize these sensations. In the clinical trial of RelieVRx, about 10% of participants reported some nausea and/or motion sickness, but these symptoms were temporary and none decided to terminate their use of the technology because of adverse events. In our preliminary data of 20 patients, no patients have reported any issues with cybersickness. Nonetheless, this will be an important risk to discuss with patients.

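### The co-primary model names only a random intercept, so the precision it reports for the 6-week arm difference rests on an unstated and unchecked covariance condition

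*Combined protocol and SAP*

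**What the plan says.** The Overview under STUDY DESIGN defines the efficacy target: "Our preliminary efficacy co-primary outcomes are (1) change in pain intensity and (2) change in opioid craving between treatment groups at 6 weeks". The section on data sources and measures fixes three occasions: "All measures will be examined at each study visit, at 0, 3 and 6 weeks".

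The Analytic plan gives each co-primary outcome a "separate 2-level mixed-effects linear regression model with the treatment arm as a mixed effect with participant-specific random intercepts", and then states: "The difference in trends of pain intensity and opioid craving will be represented by the time-by-arm interaction". Continuous secondary and biomarker outcomes follow a similar strategy. Nothing elsewhere in the document adds a random slope, a residual covariance structure, a robust standard error or a degrees-of-freedom method. Whether time is categorical or linear is not stated.

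The Power analysis paragraph bases its calculation on t-tests of change and adds: "We expect to have greater statistical power using mixed effects linear regression models with repeated measures over time". The same paragraph sets the context: "The primary purpose of this study is to test feasibility and to generate preliminary data for a future R01 application".

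**The concern.** A random intercept with independent residuals implies equal variances and equal correlations across the three visits. The co-primary contrast uses only weeks 0 and 6, but the model takes its error variance from all three visits. If measurements further apart are less correlated, the 0-6 change varies more than the pooled figure suggests and the standard error is too small. If week 3 is the noisy visit, the reverse holds.

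At stake are the confidence intervals and p-values for both co-primaries and for the other continuous outcomes. These intervals are part of the preliminary data the pilot is meant to supply. The remark about greater power bears on this too. With complete data and separate arm means at each visit, the model's estimate is the same as that of a t-test of change. Any gain in precision can then come only from the pooled error term and its extra degrees of freedom.

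The phrase describing treatment arm as a mixed effect does not relax the condition. An arm-level random effect is constant within a participant, so it cancels out of that participant's change.

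**Working it through.** **Inputs from the documents.** 40 participants randomised 1:1, so 20 per arm; visits at weeks 0, 3 and 6; the retention statement "We expect retention of approximately 85% based on our groups prior DoSA trials", which gives 0.85 × 20 = 17 completers per arm. The plan gives no figure for the precision of this model. Its 70% power refers to a t-test of change and is not used here.

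**Assumptions of this review.** All correlations and SDs, normal data, dropout completely at random, and a two-sided 5% benchmark (the plan states no alpha).

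**Step 1: formula, complete data.** Write V03, V36 and V06 for the variances of the three pairwise differences, and Vbar for their mean.

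- True variance of the arm difference in mean 0-6 change: (2/20) × V06.
- The random-intercept residual variance comes from within-person scatter after removing arm-by-visit means, on 2 × 19 × 2 = 76 df. Its expectation is Vbar/2.
- Model-based variance of the same contrast: (2/20) × 2 × Vbar/2 = (2/20) × Vbar.
- SE ratio, model to true: sqrt(Vbar/V06). It equals 1 only if V06 = Vbar.

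**Step 2: one case in full.** Correlations 0-3/0-6/3-6 of .6/.5/.6, all SDs 1. V03 = V36 = 2 − 1.2 = 0.8 and V06 = 2 − 1.0 = 1.0. Vbar = 2.6/3 = 0.867. Ratio = sqrt(0.867/1.000) = 0.931.

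**Step 3: assumed patterns** (20 per arm, 100,000 simulated trials each, t with 76 df).

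| Correlations 0-3/0-6/3-6 | SDs at 0/3/6 | V06 | Vbar | SE ratio | Type I error |
|---|---|---|---|---|---|
| .6/.5/.6 | 1/1/1 | 1.000 | 0.867 | .931 | 6.8% |
| .5/.25/.5 | 1/1/1 | 1.500 | 1.167 | .882 | 8.4% |
| .7/.5/.7 | 1/1/1 | 1.000 | 0.733 | .856 | 9.1% |
| .8/.6/.8 | 1/1/1 | 0.800 | 0.533 | .816 | 10.9% |
| .6/.5/.6 | .8/1/1 | 0.840 | 0.773 | .959 | 5.9% |
| .5/.25/.5 | .8/1/1 | 1.240 | 1.027 | .910 | 7.4% |
| .7/.5/.7 | .8/1/1 | 0.840 | 0.653 | .882 | 8.4% |
| .8/.6/.8 | .8/1/1 | 0.680 | 0.480 | .840 | 9.9% |
| .6/.6/.6 | 1/1/1 | 0.800 | 0.800 | 1.000 | 5.0% |
| .6/.6/.6 | .8/1/1 | 0.680 | 0.720 | 1.029 | 4.3% |
| .6/.6/.6 | .7/.85/1 | 0.650 | 0.617 | .974 | 5.6% |
| .5/.6/.5 | 1/1/1 | 0.800 | 0.933 | 1.080 | 3.4% |
| .6/.6/.6 | 1/1.4/1 | 0.800 | 1.120 | 1.183 | 2.1% |

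A t-test of change gives 4.9-5.1% in every row.

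**Step 4: with dropout** (20,000 trials each; per arm 17 complete, 2 lost after week 3, 1 lost after baseline; partial data kept). For the four decaying patterns, the random intercept gives 6.6/8.2/9.0/10.7% at equal SDs and 6.3/7.6/8.7/10.3% with baseline SD 0.8. An unstructured covariance with Kenward-Roger gives 4.8-5.2% in all 12 cases run and always converged.

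**Step 5: the power remark.** Mean 95% half-widths with dropout, equal SDs:

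| Pattern | Random intercept | Unstructured | Completers' t-test |
|---|---|---|---|
| .6/.5/.6 | .620 | .675 | .694 |
| .5/.25/.5 | .716 | .819 | .850 |
| .7/.5/.7 | .569 | .671 | .694 |
| .8/.6/.8 | .485 | .599 | .621 |
| .6/.6/.6 | .598 | .608 | .621 |

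Under the decaying patterns the random-intercept interval is 11/16/18/22% narrower than the t-test's, mostly because its standard error is understated. The unstructured interval is about 3-4% narrower. Under .6/.6/.6 the gains are 4% and 2%, and both are valid.

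**Step 6: why the coding of time matters to the remedy.** With a random intercept and complete data, linear and categorical time give the same 0-6 estimate. With an unstructured covariance and linear time they need not. For .6/.5/.6 and baseline SD 0.8, the generalised least squares weights on weeks 0/3/6 are −1.06/+0.11/+0.94 instead of −1/0/+1. With SDs .7/.85/1 and .8/.6/.8 they reach −1.17/+0.34/+0.83. The fitted contrast is then no longer the 6-week change defined in the Overview.

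**The case against.** The strongest reply is that no error has been shown in this trial. The documents give no variances or correlations, and the scenarios run from conservative to liberal. The largest figure, 10.9%, comes from a steep assumed decay, and the mildest decaying case with a narrower baseline is 5.9%. A random intercept is a conventional model for three visits and 40 people. Feasibility is the primary purpose, and no significance rule or go/no-go decision hangs on a p-value. A t-test of change, already used for the power calculation, would also be valid with complete data.

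Most of this stands, and it limits the weight of the point. It does not remove it: the reported interval still depends on a condition that one change of wording makes unnecessary. The t-test is a fair alternative, but it discards partial data.

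A reader might infer that the planned model inflates false positives here. The documents do not support that, because the direction depends on correlations they do not give. A reader might also infer the opposite for pain from the entry rule, "chronic pain of at least moderate pain severity (score ≥4 on the Pain, Enjoyment of Life, and General Activity (PEG) scale", since a narrowed baseline spread pushes the standard error upward. That effect is slight in the scenarios above, may be only partial because screening precedes the first study visit, and has no counterpart for craving.

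**Conclusion.** The point holds as a gap in specification, not as a demonstrated error. With complete data, the random-intercept standard error for the 6-week arm difference is correct only if V06 = Vbar, and the plan neither states nor checks this. Under the assumed patterns, type I error is about 6-11% if correlation decays with time (equal SDs or baseline SD 0.8), 5% under equal variances and correlations, and about 2-4% if week 3 is noisier or the 0-6 correlation is the highest. These ranges rest on assumed correlations and SDs and on this review's 5% benchmark.

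Only the reported precision of the preliminary efficacy results is at issue. The complete-data point estimate and the feasibility outcomes are untouched, and the logistic models are outside the point. It is a cheap improvement, between optional and recommended.

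**What to change.** In the Analytic plan, replace the random-intercept-only covariance with wording such as:

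> Time will be a categorical factor (weeks 0, 3, 6), with arm and time-by-arm, and an unstructured 3x3 within-person covariance (REML, Kenward-Roger degrees of freedom). For each co-primary outcome we will report the week-6 time-by-arm contrast, that is the between-arm difference in change from baseline to week 6, with its 95% CI. If the model does not converge, we will use the same mean model with a random intercept and a small-sample-corrected cluster-robust SE (CR2, Satterthwaite degrees of freedom).

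Categorical time is a required part of the change, for the reason in Step 6 of the working. Apply the same text to the continuous secondary and biomarker outcomes, and leave the logistic models as they are. In the dropout runs the fallback also held type I error at 4.8-5.2%.

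The change is to wording only. The statistical cost is about 38 rather than 76 error degrees of freedom (t critical value 2.024 against 1.992). If the random-intercept condition does hold, intervals are about 1.3% wider with complete data and 1.7% wider with 15% dropout (.608/.598). The model still assumes a common covariance in both arms, which matters little at 1:1 allocation.
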